6.5.6.3. Reporting Adverse Events of Clinical Interest to Sponsor/Designee

For AEs that are considered AEs of clinical interest (Section 6.5.6.1), the Sponsor or its designee should be notified within 24 hours using the appropriate eCRF.

6.5.6.4. Serious Adverse Events Require Immediate Reporting to Sponsor/Designee

An assessment of the seriousness of each AE will be made by the Investigator. Any AE and laboratory abnormality that meets the SAE criteria in Section 6.5.6.1 must be reported to the Sponsor or designee within 24 hours from the time that clinical study center staff first learns of the event. All SAEs must be reported regardless of the relationship to study drug.

The initial report should include at least the following information:

- Patient's study number
- Description and date of onset of the event
- Criterion for serious
- Preliminary assignment of relationship to study drug, and
- Investigator/site information

To report the SAE, complete the eCRF and, as applicable, the SAE form. Within 24 hours of receipt of follow-up information, the Investigator must update the eCRF and, as applicable, the SAE form. SAEs must be reported using the contact information provided in the Study Manual.

Appropriate remedial measures should be taken by the Investigator using his/her best medical judgment to treat the SAE. These measures and the patient's response to these measures should be recorded. All SAEs, regardless of relationship to study drug, will be followed by the Investigator until satisfactory resolution or the Investigator deems the SAE to be chronic or stable. Clinical, laboratory, and diagnostic measures should be employed by the Investigator as needed to adequately determine the etiology of the event.

If the Investigator becomes aware of an SAE with a suspected causal relationship to the study drug that occurs after a patient withdraws from the study, the Investigator shall report the SAE to the Sponsor or designee within 24 hours of first awareness of the event.

If the Investigator becomes aware of an SAE in a patient with a suspected causal relationship to the study drug that occurs after the end of the study, the Investigator shall report the SAE to the Sponsor within 24 hours of first awareness of the event using the paper SAE form.

6.5.6.5. Sponsor Safety Reporting to Regulatory Authorities

The Sponsor or its representative will report certain study events in an expedited manner to the Food and Drug Administration, the European Medicines Agency's EudraVigilance electronic system according to Clinical Trials Regulation (EU) No 536/2014 (CTR), and to all country Regulatory Authorities where the study is being conducted, according to local applicable regulations.

6.5.6.6. Serious Adverse Event Notification to the Institutional Review Board/Independent Ethics Committee

Suspected unexpected serious adverse reactions (SUSARs) will be reported to the IRB/IEC per their institutional policy by the Investigator or Sponsor (or Sponsor designee) according to country requirements. Copies of each report and documentation of IRB/IEC notification and acknowledgement of receipt will be kept in the Investigator's study file.

6.5.6.7. Pregnancy Reporting

If a female patient becomes pregnant during the study through the end of their Follow-up Period (defined in Section 3.1), the Investigator must report the pregnancy to the Sponsor or designee within 24 hours of being notified of the pregnancy. Details of the pregnancy will be recorded on the pregnancy reporting form. The patient should receive any necessary counseling regarding

the risks of continuing the pregnancy, the possible effects on the fetus, and be counseled to not breastfeed for 90 days after the last dose of study drug (q3M treatment arm) or color after the last dose of study drug if the patient was initially randomized to the color dose regimen (under Amendment 3) and their last dose was color vutrisiran.

The pregnancy should be followed by the Investigator until completion. At the completion of the pregnancy, the Investigator will document the outcome of the pregnancy. If the outcome of the pregnancy results in a postpartum complication, spontaneous abortion, stillbirth, neonatal death, or congenital anomaly, then the Investigator should follow the procedures for reporting an SAE as outlined in Section 6.5.6.4.

6.5.6.8. Overdose Reporting

An overdose is defined as any dose of study drug administered to or taken by a patient (accidentally or intentionally) that exceeds the highest daily dose, or is at a higher frequency, than included in the protocol. When an overdose is suspected, the Investigator should inform the Medical Monitor.

6.5.7. COVID-19 Data Collection

Information on the COVID-19 infection status of the patient, if known, and other information on the impact of the COVID-19 pandemic on the patient's participation in the study will be collected.

7. STATISTICS

A Statistical Analysis Plan (SAP) will be finalized before study unblinding for the primary analysis. The SAP will detail the implementation of the statistical analyses in accordance with the principal features stated in the protocol.

7.1. Determination of Sample Size

7.2. Statistical Methodology

The statistical and analytical plans presented below are brief summaries of planned analyses for the primary analysis, conducted at the completion of the DB Period (Section 3.1). Changes to the methods described in the final SAP will be described and justified as needed in the clinical study report. For information on study endpoints, see Section 2.

Additional analyses and data summaries will be outlined in the SAP.

7.2.1. Populations to be Analyzed

The populations (analysis sets) are defined as follows:

- Full Analysis Set (FAS): All patients who were randomized and received any amount of study drug (vutrisiran or placebo).
- **Vutrisiran Monotherapy Subgroup FAS:** All patients who were not on tafamidis at the study baseline in the FAS.
- Safety Analysis Set: All patients who received any amount of study drug.
- Vutrisiran Monotherapy Subgroup Safety Analysis Set: All patients who were not on tafamidis at the study baseline in the Safety Analysis Set.
- **PK Analysis Set:** All patients who received at least one full dose of study drug and have at least one non-missing postdose PK assessment and evaluable PK data.
- **PD Analysis Set:** All patients who received at least one full dose of study drug and have an evaluable baseline and at least one evaluable postbaseline sample for TTR assessment.

The FAS and vutrisiran monotherapy subgroup FAS will be used for the analysis of efficacy endpoints. Safety analyses will be based on the Safety Analysis Set and vutrisiran monotherapy subgroup Safety Analysis Set. PK and PD analyses will be based on PK Analysis Set and PD Analysis Set, respectively.

All by-treatment analyses based on the FAS and vutrisiran monotherapy subgroup FAS will be according to the randomized treatment arm. Safety analyses will be analyzed according to the treatment actually received.

7.2.2. Examination of Subgroups

Subgroup analyses will be conducted for the primary and secondary efficacy endpoints. Efficacy subgroup analyses will be conducted for age group (<75 versus ≥75), baseline tafamidis use (Yes versus No) (overall population endpoints only), ATTR disease type (hATTR; wtATTR) and NYHA Class (I/II; III). Safety subgroup analyses will be conducted for at least the following variables: age group, gender, race, geographic region, and NYHA class. Additional variables may be included and the details will be provided in the SAP.

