CV events will include recurrent CV hospitalizations and recurrent non-hospitalized urgent HF visits in accordance with the 2017 Cardiovascular and Stroke Endpoint Definitions for Clinical Trials.[Hicks 2018] The primary endpoints will provide definitive evidence of a clinically meaningful impact in the study population. Similar endpoints have been used in numerous heart failure studies, including the recent Phase 3 ATTR-ACT study of the TTR tetramer stabilizer, tafamidis.[Maurer 2018; McMurray 2019] Including urgent HF visits will account for the likelihood that the COVID-19 pandemic may increase current trends to reduce hospitalizations and shift management of clinically comparable heart failure events to outpatient settings.[Hicks 2018] Including urgent HF visits also accounts for regional differences in the criteria for hospitalization, which may be further exacerbated by the COVID-19 pandemic. In addition, data support the equivalence of urgent HF visits to HF hospitalizations for predicting mortality.[Okumura 2016]

As a key secondary objective, the study will also evaluate the efficacy of vutrisiran on functional capacity (6-minute walk test; 6-MWT) and health status and health-related quality of life (Kansas City Cardiomyopathy Questionnaire Overall Summary; KCCQ-OS). The 6-MWT is a clinically relevant assessment of functional capacity that has been used as a primary endpoint in pivotal clinical trials in pulmonary arterial hypertension [Gabler 2012] and has been used in the evaluation of patients with HF.[Bittner 1993; Flynn 2009; Flynn 2012; Mangla 2013; Masoudi 2004; Maurer 2018] The KCCQ-OS has been used as a common assessment in HF interventional studies and has been shown to be an independent predictor of prognosis in HF.[Heidenreich 2006]

Both 6-MWT and KCCQ-OS were shown to rapidly and consistently decline over time in cardiac ATTR amyloidosis patients and, in the tafamidis Phase 3 ATTR-ACT study, these

measures were used to demonstrate a reduction of decline with tafamidis treatment.[Maurer 2018] These data support the use of 6-MWT and KCCQ-OS as clinically relevant endpoints.

The inclusion of placebo as a control for this study allows for a rigorous analysis of the treatment effect of vutrisiran. A placebo control will be especially useful in characterizing the efficacy and safety of vutrisiran in a patient population which is prone to cardiac events.

[figure not shown]

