10.4. Amendment History

10.4.1. Amendment 5 Summary of Changes

The primary purpose for this global protocol amendment is to expand the analysis of the existing primary endpoint to both the overall population and the vutrisiran monotherapy subgroup (defined as the subgroup of patients not on tafamidis at study baseline). Changes included in this amendment concern the method of data analyses and do not impact study execution or the patient experience.

Establishing the efficacy of vutrisiran in the overall population is important because it is representative of current treatment practice, wherein many patients with ATTR amyloidosis (hereditary and wt) with cardiomyopathy are prescribed tafamidis as it is the only currently approved treatment available.

The rationale for analyzing the primary endpoint in the vutrisiran monotherapy subgroup is to enable demonstration of the potential clinical benefit of vutrisiran without any confounding effect of benefit from tafamidis. Patients already prescribed tafamidis for the approved cardiomyopathy indication were permitted to enroll in HELIOS-B, and there was no eligibility requirement that these patients needed to have manifested disease progression on tafamidis. Thus, patients on tafamidis at baseline, comprising approximately 40% of the enrollment into

HELIOS-B, are likely to have been receiving some degree of CV benefit from this medication throughout the trial. For this reason, the results from a pre-specified analysis in the vutrisiran monotherapy subgroup would provide the clearest demonstration of the potential clinical benefit of vutrisiran, without any confounding effect of benefit from concomitant tafamidis.

This amendment also restructures the existing secondary and exploratory endpoints such that specific endpoints were moved from exploratory to secondary and from secondary to exploratory based on the rationale below.

Changes included with Amendment 5 are outlined below:

Section(s)	Description of Change	Brief Rationale

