5.7. Efficacy Analyses

Efficacy endpoints will be analyzed using the FAS and mono-FAS. As an important subgroup, efficacy endpoints will also be analyzed in the background tafamidis subgroup. Therefore, unless otherwise specified, all efficacy analyses will be presented by treatment groups in the overall population, vutrisiran monotherapy subgroup and background tafamidis subgroup. The vutrisiran monotherapy subgroup and background tafamidis subgroup analyses are based on subgroup data only. In general, the same statistical model will be used for analyzing the efficacy endpoint for overall population, the vutrisiran monotherapy subgroup and the background tafamidis subgroup,

with the exception that in the analysis of the overall population, baseline tafamidis use will be used as an additional covariates or stratification factor.

For covariates used in the statistical models, unless noted otherwise, the categorizations will be based on ATTR disease type (hATTR vs. wtATTR), NYHA Class (I/II vs. III), age group (<75 vs. >=75) and baseline NT-proBNP group (<=3000 ng/L, >3000 ng/L). **CCI**

For composite endpoints, mean cumulative function (MCF) plots by treatment groups will be generated. For longitudinal endpoints, least square mean (+/- SEM) over time by treatment groups will be plotted. For time to event endpoints, Kaplan-Meier (KM) plots by treatment groups will be generated.

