5.7.4. Evaluation of Subgroups

All analysis and summary results are presented by baseline tafamidis use subgroups, with vutrisiran monotherapy subgroup defined as an analysis population and background tafamidis defined as a key subgroup. Additionally, subgroup analyses will be conducted to assess the consistency of treatment effect within various subgroups defined by baseline characteristics as listed in the following table.

Subgroup	Overall population	Vutrisiran Monotherapy subgroup
Baseline tafamidis use (yes; no)	Yes	N/A
Age group (<75; ≥75)	Yes	Yes
ATTR disease type (hATTR; wtATTR)	Yes	Yes
NYHA class (I/II; III)	Yes	Yes
Baseline NT-proBNP (≤2000; >2000 ng/L)	Yes	Yes

Subgroup analyses will be performed for the composite endpoint of all-cause mortality and recurrent CV events, 6-MWT, KCCQ-OS, all-cause mortality, NYHA class, and recurrent CV events in both the overall population and vutrisiran monotherapy subgroup. The analyses will be conducted based on the subgroup data only.

- Composite endpoint of all-cause mortality and recurrent CV events:

Composite endpoint of all-cause mortality and recurrent CV events will be analyzed by LWYY model including treatment and baseline NT-proBNP as covariate. For subgroup analysis in the overall population, the model will also be stratified by baseline tafamidis use.

- Change from baseline in 6-MWT and KCCQ-OS:

Change from baseline in 6-MWT and KCCQ-OS will be analyzed by MMRM model with baseline value as a covariate, and treatment, visit, treatment-by-visit interaction as fixed effects. For subgroup analyses in the overall population, the model will also include baseline tafamidis use as a fixed factor.

- CCI [REDACTED]

- Change from baseline in NYHA class:

The binary outcome (stable or improved vs. worsened in NYHA Class at Month 30) will be analyzed by a CMH method stratified by baseline NT-proBNP. For subgroup analysis in the overall population, the model will also be stratified by baseline tafamidis use.

- Recurrent CV events:

The frequency of CV events will be analyzed by Poisson regression including treatment and baseline NT-proBNP as covariates. For subgroup analysis in the overall population, the model will also include baseline tafamidis use as a covariate.

Forest plots will be generated to illustrate the estimated treatment effect along with 95% CI within each subgroup.

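### The subgroup analyses aim to judge consistency of effect, but the readable plan commits to no reported estimate of how the effect differs between subgroup levels

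*Protocol*

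**What the plan says.** Protocol section 7.2.2 commits to the analyses ("Subgroup analyses will be conducted for the primary and secondary efficacy endpoints"), names age, baseline tafamidis use, ATTR disease type and NYHA class as efficacy factors, and gives no method.

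SAP section 5.7.4 adds baseline NT-proBNP and states the purpose: "subgroup analyses will be conducted to assess the consistency of treatment effect within various subgroups defined by baseline characteristics". On method it says: "The analyses will be conducted based on the subgroup data only". For example, the composite endpoint "will be analyzed by LWYY model including treatment and baseline NT-proBNP as covariate", with tafamidis stratification added in the overall population. The output is a forest plot with an estimate and 95% CI for each subgroup.

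SAP section 5.7 treats the tafamidis groups the same way: "The vutrisiran monotherapy subgroup and background tafamidis subgroup analyses are based on subgroup data only".

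On why tafamidis matters, Protocol section 1.5 justifies a longer follow-up than an earlier tafamidis trial by noting that tafamidis taken alongside could shrink the overall vutrisiran effect. Protocol section 10.4.1 puts about 40% of enrolled patients on tafamidis at baseline and says they "are likely to have been receiving some degree of CV benefit from this medication".

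**The concern.** Consistency is a statement about the difference between two subgroup effects. Two separate estimates, each with its own CI, do not state that difference or its uncertainty. When the contrast is not printed, the usual habit is to compare which rows exclude the null, and that mostly reflects how many patients or events each row holds.

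The risk is a claim that the drug works in one group and not in another when the data show nothing of the kind. The opposite risk is a claim of consistency when the data could not have shown a difference. Tafamidis is the factor where this matters most, because the protocol itself raises it as something that may alter the effect. The two primary populations do not supply the contrast either: the monotherapy group lies inside the overall population, so those two results are not independent.

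**Working it through.** **Which readable models contain a treatment-by-subgroup term**

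- Age, ATTR disease type, NYHA class, NT-proBNP: none, in SAP 5.7.4 or in any other readable model.
- Baseline tafamidis use, overall population: present in the Poisson model for recurrent CV events (SAP 5.7.1.3), the repeated-measures sensitivity analysis of NYHA class (SAP 5.7.2.3.3) and the pattern-mixture ANCOVA for 6-MWT and KCCQ-OS (SAP Appendix 9.4). None of these sections says the term will be reported or used to judge consistency.
- Protocol 7.2.5.2 has the term in a logistic model for NYHA class, but SAP 5.7.2.3.2 replaces that model with a CMH analysis.
- Not determinable: the primary models for the composite (SAP 5.7.1.2), for 6-MWT and KCCQ-OS (5.7.2.1.2) and for mortality (5.7.2.2.2), and one bullet of 5.7.4, are redacted.

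**Inputs for the size**

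The plan states no figure on this point, and the sample-size assumptions in SAP 2.6 are redacted, so there is nothing to reproduce.

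- From the documents: about 40% on tafamidis (Protocol 10.4.1), so about 60% not; about 20% hATTR and 80% wtATTR (Protocol 3.1).
- Assumed: overall power of 80% or 90% at two-sided 0.05; the same true effect in every subgroup; statistical information proportional to the number of patients; normal approximation, counting significance in the direction of benefit.

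**How often the two rows disagree under one uniform effect**

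The overall expected z is m = 1.960 + z(power), which is 2.802 at 80% and 3.242 at 90%. A row with share f has expected z of m√f and reaches p<0.05 with probability Φ(m√f − 1.960). With row probabilities p1 and p2, exactly one row is significant with probability p1(1 − p2) + p2(1 − p1).

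- 40:60, 80% power: p1 = Φ(1.772 − 1.960) = 0.425; p2 = Φ(2.170 − 1.960) = 0.583; 0.425 × 0.417 + 0.583 × 0.575 = 0.512.
- 40:60, 90% power: p1 = 0.536; p2 = 0.709; 0.536 × 0.291 + 0.709 × 0.464 = 0.485.
- 20:80, 80% power: p1 = 0.240; p2 = 0.707; 0.240 × 0.293 + 0.707 × 0.760 = 0.608.
- 20:80, 90% power: p1 = 0.305; p2 = 0.826; 0.305 × 0.174 + 0.826 × 0.695 = 0.627.

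**What the contrast could show**

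SE(contrast) / SE(overall) = √(1/f + 1/(1 − f)).

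- 40:60: √(2.5 + 1.667) = 2.04.
- 20:80: √(5 + 1.25) = 2.50.

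Even if the full effect were present at one level and absent at the other, the nominal test would have power Φ(m/ratio − 1.960): 27.8% and 35.5% for tafamidis, 20.1% and 25.4% for hATTR versus wtATTR, with m taken at 80% and 90% overall power. A non-significant contrast is therefore weak evidence of sameness.

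**How many contrasts**

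There are five factors in the overall population, four in the monotherapy subgroup and six endpoints: (5 + 4) × 6 = 54. For one endpoint with no true heterogeneity, treating the tests as independent, the chance of at least one nominal p<0.05 is 1 − 0.95⁵ = 22.6% in the overall population and 1 − 0.95⁴ = 18.5% in the monotherapy subgroup.

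**The case against.** The best reply has four parts.

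- The levels of a factor share no patients, so a reader can take the difference of the two log hazard ratios and add the squared standard errors recovered from the CIs. This stands. A reader might infer from SAP 5.7.4 that chance and real differences cannot be separated at all, and that would be too strong. What is missing is a prespecified, printed contrast and a rule for reading it.
- Treatment-by-tafamidis terms are already in several models and may be in the redacted primary ones. This also stands. A reader might infer that the trial has no tafamidis contrast at all, and the documents do not support that. Table and figure shells are separate documents (SAP section 1), so the estimate may be printed; no readable text promises it.
- The discordance figures describe how readers behave, not a decision rule in the plan, and SAP 4.6 gives subgroups no alpha. Correct: they show how misleading the rows can look, not an error rate of the trial.
- The contrasts are weak and numerous. Correct, which is why they should be estimates with CIs and not pass/fail tests.

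Two further inferences should be resisted. Protocol 10.4.1 does not say that the vutrisiran effect is smaller on tafamidis; it argues that background benefit confounds the picture. The remark in section 1.5 is nearer, and it concerns the overall effect. Nor does the protocol expose a gap on region: "Including urgent HF visits also accounts for regional differences in the criteria for hospitalization" describes a step already taken to deal with regional differences, so an efficacy subgroup by region would be a preference.

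**Conclusion.** The point holds as a cheap improvement. In the readable text of SAP 5.7.4 the stated aim and the method do not match: no difference in effect is estimated for age, ATTR disease type, NYHA class or NT-proBNP, and for baseline tafamidis use no readable section commits to reporting the terms already fitted. Nothing is claimed about the redacted models.

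For scale, under a uniform effect the two tafamidis rows would disagree on p<0.05 in about half of trials, and the hATTR and wtATTR rows in just over 60%. These figures rest on the assumed 80% to 90% power and on information following patient numbers; if event rates differ between groups, the effective splits shift. No figure is offered across several factors together, because the documents do not give the splits for age, NYHA class or NT-proBNP. The primary and secondary tests are unaffected.

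**What to change.** Keep the subgroup-only estimates. In SAP 5.7.4, for each listed factor, add a treatment-by-subgroup contrast using the endpoint's own method: a ratio of hazard ratios or rates, or a difference in effects (for NYHA class, the difference between the two CMH risk differences). Print it with a 95% CI and nominal p-value beside each pair in the forest plot. Begin with baseline tafamidis use on the primary composite. Commit to reporting the treatment-by-tafamidis estimates from the models that already contain the term.

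Add a sentence that the contrasts are descriptive and unadjusted for multiplicity, and that a non-significant contrast is not evidence of consistency, since its standard error is about 2.04 times (40:60) to 2.5 times (20:80) the overall one.

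The cost is SAP wording and up to 54 contrasts from data already collected. The downside is that they will be imprecise and, being many, some will look notable by chance. Alpha, trial conduct and patients are unaffected.
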